Postoperative variables are defined as those that are recorded after the second stage of the Masquelet or the index CTMC defect reconstructive procedure. They include clinical examination, imaging, pain and limb function assessment, and the overall treatment outcome (questionnaires). The followup data are collected at hospital discharge, at 2 weeks, 6 weeks, 3 months, 6 months, 12 months and 18 months post defect reconstruction surgery. Postoperative complications and/or adverse events will be documented and reported.

Defect Healing Assessment

The radiographic determination of defect healing will consist of a 5-grade scale (ranging from no healing to completely healed) in quarter defect length increments (ie, 0%, 24%, 50%, 75%, 100% defect healed). The radiographic review will be conducted by the PIs and 2 independent reviewers. Inter- and intrarater agreement will be calculated for the final determination of the defect healing status.

CT imaging will be performed routinely at 12 months post defect reconstruction surgery to visualize the new bone formation/graft reconstitution within the defect using two- and three-dimensional reconstructions. Spatial determination of new bone formation will be carried out in relation to the defect, the hardware, and the local

anatomic landmarks. The quantitative (bone volume) and qualitative (mineral density) will be calculated following a metallic hardware (cage, nail, plate-screws) subtraction algorithm.

Questionnaires

Questionnaires will be used in the study as outcome instruments for defining the safety characteristics of the enrolled subjects; determining the longitudinal impact on health changes, function and satisfaction; delineating the effectiveness of the Masquelet versus CTMC technique of defect reconstruction; developing of specific evidence-based medicine clinical pathways and guidelines.

The following questionnaires will be used in the study as outcome instruments: □

Brief Pain Inventory Short Form (Cleeland 1994);

- Disabilities of the Arm, Shoulder, and Hand (DASH) for the upper extremity (Hudak 1996);
- Lower Limb Core Scale (LLCS) for the lower extremity (Johanson 2004);
- Medical Outcomes Survey Short-Form 36 (SF-36) (Ware 1996);
- Time Trade-Off to assess Quality-Adjusted Life Years (QALY) (Torrance 1987).

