progress in defect healing and/or functional restoration in relation to the treatment time and finally to the costs and/or resources allocated to achieve that. Our expectation is that clinical outcomes will favor the CTMC technique because of its single stage surgery, shorter treatment time, efficacious defect healing, and early unrestricted functional restoration. It is important to emphasize that the primary determination in the study is to establish whether applying one of the treatment arms versus the other is associated with clinically- and/or statistically-significant improvement in outcome, and secondarily assess the time, cost, and resources that enabled that improvement. Both the estimated outcome and cost differences can exhibit some variation, however, accounting for uncertainty in estimates has become an important component of economic evaluation. Derived from the joint distribution of costs and effects, cost-effectiveness acceptability curves (CEACs) will be established to summarize the uncertainty in cost-effectiveness estimations. This is particularly important if the study arm is found to be cost-effective rather than cost-saving.

HUMAN SUBJECT RECRUITMENT AND SAFETY PROCEDURES

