- Commercially-available, freeze-dried cancellous bone croutons approved for clinical application will be used. The Allograft (tissue) tracking number will be recorded. No preference will be given to the allograft provider on condition that it is in compliance with regulations and guidelines established by the FDA and the American Association of Tissue Banks. The intraoperative allograft handling and its application will strictly follow the provider's recommendations. The volume of the cancellous croutons should be sufficient to pack the cage.
- Demineralized bone matrix (DBM; Grafton PuttyTM; Osteotech®, Eatontown, NJ, USA) is allogeneic bone extract without bone mineral component. DBM demonstrates inherent osteoinductive properties, ie it induces *de novo* bone formation. DBM putty will be used in the study consistently. To eliminate inherent differences in osteoinductive properties that may occur between DBMs supplied by various vendors, in the trial consistently DBM putty supplied by Osteotech will be used. Grafton PuttyTM has gained FDA clearance/exempt for clinical use and it will be applied in full compliance and following the guidelines of the American Association of Tissue Banks. Grafton putty has well documented osteoinductive properties and it is the only DBM currently available on the market with clinical efficacy assessed and validated in a prospective clinical trial (Lindsey 2006). DBM putty will be uniformly mixed with allograft croutons in a ratio of approximately 1-to-3. The cancellous croutons-DBM composite will be used as the graft Option B to pack either the space within the biomembrane in the Masquelet technique or the cage in the CTMC technique.

Study-Specific Procedure Algorithm

Pre-, Intra-, and Post-operative Data Collection

	Clinical Exam	Imaging	Pain Score	Functional Assessment	Outcome Measure	QALY	Adverse Event
Preoperative	✓	X-ray	✓	✓	✓	✓	
Intraoperative	✓						✓
Postoperative							
Immediate postop	✓	X-ray					✓
2 weeks	✓	X-ray	✓	✓			✓
6 weeks	✓	X-ray	✓	✓			✓
3 months	✓	X-ray	✓	✓	✓		✓
6 months	✓	X-ray	✓	✓	✓		✓
12 months	✓	X-ray CT	✓	✓	✓	✓	✓
18 months	✓	X-ray	✓	✓	✓	✓	✓

DATA MANAGEMENT:

Methods of Data Collection

A study specific Case Report Form (CRF) will be designed in accordance to the following principles:

- has unique coded subject study identifier (ID);
- is consistent with the study protocol;
- gathers study data accurately and reliably;
- organizes and labels forms and fields to permit intuitive data entry;

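### The time trade-off is scheduled only before surgery and at 12 and 18 months, so any QALY comparison would miss a utility difference that opens after surgery and closes within the first year

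*Protocol*

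**What the plan says.** The visit-by-visit schedule is the table in the Protocol section Study-Specific Procedure Algorithm, under "Pre-, Intra-, and Post-operative Data Collection". Its columns are "Clinical Exam Imaging Pain Score Functional Assessment Outcome Measure QALY Adverse Event", so QALY is separate from the general outcome measure. The QALY column is ticked preoperatively, at 12 months and at 18 months. It is blank at 2 weeks, 6 weeks, 3 months and 6 months. Pain and function are ticked at all four of those visits, and the outcome measure at 3 and 6 months.

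The Protocol's Questionnaires section names the time trade-off as the source of QALYs and links no other instrument to them. The same section says, less precisely, that questionnaires are completed at a first, a middle and a last visit. Subject Reimbursement for Study-Related Expenses pays extra for the time taken at 2 weeks, 12 months and 18 months.

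Under Resources Expenditure and Cost-Effectiveness Analysis, the sponsor expects outcomes to favour CTMC because of single-stage surgery, "shorter treatment time, efficacious defect healing, and early unrestricted functional restoration". The Background in the data and safety monitoring plan contrasts this with a second operation and a longer period of restricted loading after Masquelet. The cost-effectiveness section also says that "cost-effectiveness acceptability curves (CEACs) will be established to summarize the uncertainty in cost-effectiveness estimations". Neither document states how QALYs are to be calculated between visits, and the SAP does not mention them.

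**The concern.** A QALY total is the area under a patient's utility curve. With utility measured at baseline and next at 12 months, the first year is known only from its two ends. Much of the sponsor's case for CTMC lies inside that year: loading as tolerated from the start, against gradual lower-limb loading from about 6 weeks after grafting in the Masquelet arm. If the arms have come together by 12 months, the schedule cannot show that one arm spent the intervening months in better health. More patients would not help, because the information is never collected, and it cannot be recovered afterwards.

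Cost-effectiveness is part of the overall objective and one of the specific aims, so a QALY comparison that is blind to this period would weaken a stated aim. The primary clinical comparison is not affected.

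**Working it through.** The documents give no QALY figure, so there is nothing to reproduce. The check is a reading of the table followed by illustrative arithmetic.

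**Coverage.** Pain and function are scored at 7 times (preoperatively, 2 weeks, 6 weeks, 3, 6, 12 and 18 months). The time trade-off is taken at 3 of them. The interval with no interior measurement is 12 of 18 months, or 67%.

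**What the planned schedule returns.** Let d(t) be the utility difference, CTMC minus Masquelet. By the trapezoid rule on 0, 12 and 18 months, in years:

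QALY difference = 1.0 × (d0 + d12)/2 + 0.5 × (d12 + d18)/2.

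If d0 = d12 = d18 = 0, this is 0 whatever happens in between.

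**What that could leave out.** Adding measurements at 3 and 6 months, with zero difference at 0 and 12:

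0.25 × d3/2 + 0.25 × (d3 + d6)/2 + 0.5 × d6/2 = 0.25 × d3 + 0.375 × d6.

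The differences are assumed:

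| d3 | d6 | QALY difference | Planned schedule |
|---|---|---|---|
| 0.05 | 0.05 | 0.0125 + 0.01875 = 0.031 | 0 |
| 0.20 | 0.10 | 0.050 + 0.0375 = 0.0875 | 0 |
| 0.20 | 0.20 | 0.050 + 0.075 = 0.125 | 0 |

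**Which visits matter.** Now assume a difference that reaches a peak of 0.10 by 2 weeks (0.46 months), holds to time P, and falls in a straight line to zero at time E. The area is 0.10 × (P + E − 0.46)/24, with times in months. The column adding 3 and 6 months uses the formula above. The column that also adds 6 weeks (1.38 months) is the trapezoid over 0, 1.38, 3, 6 and 12 months.

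| P, E (months) | Area under assumed curve | Planned | Add 3 and 6 months | Add 6 weeks, 3 and 6 months |
|---|---|---|---|---|
| 1.38, 3 | 0.10 × 3.92/24 = 0.016 | 0 | 0 | (0.069 + 0.081)/12 = 0.0125 |
| 3, 6 | 0.10 × 8.54/24 = 0.036 | 0 | 0.025 | (0.069 + 0.162 + 0.150)/12 = 0.032 |
| 6, 12 | 0.10 × 17.54/24 = 0.073 | 0 | 0.0625 | (0.069 + 0.162 + 0.300 + 0.300)/12 = 0.069 |

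Adding 2 weeks as well recovers the full area under these curves. The areas scale with the peak: peaks of 0.05 to 0.20 give 0.008 to 0.146 across the three shapes. Adding only 3 and 6 months would still miss a difference that is gone by 3 months.

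**A lasting difference.** If 0.10 is reached by 2 weeks and held to 18 months, the area is 0.10 × (18 − 0.23)/12 = 0.148. The planned schedule returns (12 × 0.05 + 6 × 0.10)/12 = 0.100. This is partly captured.

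**If the extra payment at 2 weeks means a time trade-off then.** With the 0.10 peak and a line from 2 weeks to 12 months, the estimate is 12 × 0.05/12 = 0.050 for all three shapes, against 0.016, 0.036 and 0.073. The gap from 2 weeks to 12 months would remain.

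**Clock.** Study Variables counts postoperative time from the second Masquelet stage but from the single CTMC operation. Course of Action puts 6 to 8 weeks between the Masquelet stages. At 4.348 weeks per month that is 1.38 to 1.84 months. From first reconstructive surgery to the 12-month visit is therefore about 13.4 to 13.8 months for Masquelet and 12 for CTMC. An assumed utility gap of 0.05 to 0.20 during the spacer period alone is worth 0.05 × 6/52.18 = 0.006 to 0.20 × 8/52.18 = 0.031 QALY, and no time trade-off falls within it.

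**The case against.** The strongest reply is that a reader might infer that the acceptability curves would be driven by cost alone. The documents do not support that. The cost-effectiveness section describes the effect as progress in healing or in restored function, set against treatment time and cost, and never names the QALY as the effect. Function is scored and radiographs are taken at all the early visits, so the named effects are measured when the arms are expected to differ. This stands, and it confines the point to a QALY-based comparison.

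Several smaller objections also stand:

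- The straight line is an inference. No rule is stated; linear interpolation is the usual choice when nothing is measured in between.
- Every utility value above is assumed. The sponsor also expects better healing, and an advantage that lasts would be seen in part. Upper-limb defects are eligible, and the weight-bearing argument is weaker there.
- With 15 per arm, the 95% half-width for a QALY difference is about 2.048 × √(2/15) × SD = 0.75 × SD, or 0.075 to 0.22 for assumed SDs of 0.10 to 0.30. Many of the illustrated differences lie within that noise. That limits what this trial can show; it does not justify a schedule that sets the estimate to zero by construction.
- That the time trade-off is taken only at these three times rests on the table. The other two statements on timing are looser, but neither names a visit between 2 weeks and 12 months.

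The SF-36 is among the questionnaires, but neither document plans to derive utilities from it.

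**Conclusion.** The point holds in a limited form. As scheduled, the time trade-off cannot show a utility difference that opens after surgery and closes by 12 months. Under linear interpolation such a difference contributes exactly 0, whatever its size. For assumed advantages at 3 and 6 months of 0.05/0.05 to 0.20/0.20, the amount missed is 0.03 to 0.125 QALY. These figures illustrate scale and do not estimate the bias in this trial. They rest on equal utilities at 0, 12 and 18 months, on linear interpolation, and on utility values that the documents do not supply.

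A reader might go further and conclude that the whole expected CTMC advantage goes unmeasured, or that the cost-effectiveness analysis as a whole fails. Neither follows: lasting differences are partly captured, and healing and function, the effects the Protocol names, are followed from the start. The unequal time origin is a related defect in the same comparison. This is a worthwhile and inexpensive improvement to a secondary aim.

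**What to change.** 1. Tick QALY at the existing 2-week, 6-week, 3-month and 6-month visits. If burden forces a choice, keep 6 weeks, 3 months and 6 months.
2. State in the SAP that QALYs are the area under all measured points, with linear interpolation, and say whether they enter the acceptability curves or are reported separately.
3. Start the QALY and cost clocks at one origin in both arms, either randomization or first reconstructive surgery, and use the same time horizon from that origin. If the origin is first surgery and the horizon 18 months, the Masquelet value at the horizon is interpolated, because that arm's 18-month visit falls at about 19.4 to 19.8 months (18 + 1.38 to 18 + 1.84). A time trade-off between the stages would avoid interpolating across the spacer period as well.
4. Reconcile the table with the Questionnaires wording on first, middle and last visits, and with the extra payment for time at 2 weeks, 12 months and 18 months.

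The cost is one more instrument at visits where pain and function are already scored: at most 30 × 4 = 120 extra administrations, or 90 for the three-visit minimum, plus the matching case report form entries. The downside is a small added burden on patients. The Protocol gives about 30 minutes for all the questionnaires together and no separate time for the time trade-off. An inter-stage measurement would add to this in the Masquelet arm.

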NCT 02015390

**The Comparative Efficacy of the Masquelet versus Titanium Mesh Cage
Reconstruction Techniques for the Treatment of Large Long Bone Deficiencies**

PI: [name], PhD
[name]

The University of Texas Medical Branch; Galveston, TX

Jun 22, 2020

STATISTICAL PLAN AND DATA ANALYSIS:

Statistical Methodology

Descriptive statistics will be used to analyze the collected data specifically to:

- characterize the patient with segmental bone deficiency;
- estimate the proportion of healing with/without complications;
- cross-compare the recorded variables.

Paired Student t-test will be used to test the effects of the Masquelet versus the CTMC defect reconstruction on the outcome measures.

Analysis of covariance (ANCOVA) will be used for pair-wise comparison within the two treatment arms (graft Option A vs. Option B).

A mixed model for repeated measures will be conducted to evaluate:

- the effect of the Masquelet versus CTMC defect reconstruction on the outcome measures, adjusting for patient demographics and clinical characteristics;
- the effect of the specific defect characteristics (etiology, size, location, adjacent soft tissue involvement, etc) on the treatment outcome;
- the possible interaction effects between treatment and defect characteristics.

Multiple models will be used in case the proposed sample size would not have enough power to produce an accurate predictive model which accounts for all possible morbidities and interactions. Simple models using modern penalty function techniques (lasso, elastic net, boosted trees, etc.) to control model complexity should provide a useful initial predictive tool for each clinical and quality of life outcome.

Both receiver operating curve (ROC) analysis and clinical judgment will be used in determining the optimal clinical indications and timing for defect reconstitution with the definitive defect reconstruction using the Masquelet versus the CTMC technique.

Sample Size Justification

Based on the data from the PIs' preliminary clinical series of 20 patients, it can be assumed that 75% of patients with segmental bone defects reconstructed with the CTMC technique will heal without complications. In the present study we propose to enroll and follow-up 30 patients throughout 4 years of the clinical trial duration.

This sample size of 30 is largely determined by clinical feasibility. For the sample size 30, a two-sided 95% confidence interval for a single proportion using the large sample normal approximation will extend 0.134 from the observed proportion for an expected proportion of 0.75.

Our past experience with a prospectively investigating 20 patients with traumatic segmental defects presented to our institution (single site) within 3.5-year period suggests that the 30 patients to be enrolled in the proposed study within the anticipated time frame is very feasible considering broader inclusion criteria and multi-site study location.

Data Analysis

Prospectively collecting pertinent pre-, intra-, and postoperative study variables will establish a database of patients with segmental bone defects reconstructed with CTMC in combination with bone graft or bone graft substitute. A series of multivariate models will be constructed to model sizeable complex interactions between the patient, defect etiology and characteristics, process of care variables and surgical outcomes. Specific analyses will be performed to address the following questions:

- What are the characteristics of the patients who present with segmental bone deficiency warranting surgical reconstruction that achieve superior functional and quality of life outcomes when treated with the Masquelet versus the CTMC technique?
- What is the nature of a segmental bone defect and its related variables that determine superior outcomes after the Masquelet versus the CTMC reconstruction?
- What are the aspects of pre-, intra-, and postoperative care that differ for patients who:
 - A) achieve poor outcomes;
 - B) sustain treatment related complications;
 - C) incur resource usage well in excess of the average?

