The treatment cost calculations for patients treated with the Masquelet (Arm I) or the CTMC technique (Arm II) in combination with auto- (Option A) or allograft (Option B) will include the length of hospital stay, overall treatment cost, and the comparative cost-efficiency assessment. The clinical characteristics of the study arms will be reported with means and standard deviations, frequencies, or percents, when appropriate. All analyses of outcomes will be performed both as "intent-to-treat" and as "efficacy." Average charges in the two groups will be compared with a Student t-test or Wilcoxon rank sum test. The progression of defect healing based on imaging evaluation (using both qualitative and quantitative measures) and functional recovery assessment (both subjective questionnaire, and objective outcome scores) will be compared with the log-rank test and proportional hazards model. Frequencies of repeat surgical intervention and complications will be compared with chi-square tests. Because there are two designated expert surgeons who will each be performing a single study arm, consistency could be expected within each treatment arm as it relates to the specifics of the surgical intervention and the post-surgical course of patient management.

The standard economic evaluation approach to assessing the difference between the two defect treatment arms is to construct a comparative cost-effectiveness ratio for each arm. This will include determining the incremental

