- Provide a thorough characterization of the patient population that presents with segmental bone defects that warrant surgical reconstruction (specific aim 1);
- Establish defect characteristics among the study subjects treated with the Masquelet versus the CTMC procedure (part of specific aim 2);
- Collect and analyze the distribution of patients within specific study arms (Option A vs Option B) (part of specific aim 3);
- Establish the cost or preoperative and surgical management of the study subjects;
- Provide an analysis of patients with segmental bone deficiency who did not meet study eligibility criteria;
 - Establish the extent of patient compliance with immediate and early postoperative regimen.

3. Study Follow-up Period (18 months)

This period encompasses the timeframe of the last 18 months, i.e. from termination of enrollment to study completion. This period's primary objective is to successfully complete follow-up of all enrolled patients. During this period the following study tasks are expected to be accomplished:

- Continuing postoperative data collection;
- Analysis of data collection process (consistency, redundancy, dropout rate);
- Tentative statistical analysis of the collected data;
- Establish costs of subject follow-up incurred;
- Itemize all resource expenditure for total treatment costs assessment.

Milestone #4: Follow-up completion of 30 study subjects

4. Study Post Completion Period (2-4 months)

This period encompasses the timeframe after the study has been terminated. The research efforts in this period include:

- Thorough analysis of all pre-, intra-, and postoperative variables collected in the study to accomplish the specific study aims 2, 3 and 4.
- Assessment of the safety and efficacy of the CTMC defect reconstructive technique
- Establishing the clinical indications and treatment recommendation for CTMC the based upon the treatment outcome;
- Assessment of the total resource expenditure related to the CTMC reconstruction technique (in accordance with the graft option type) and comparison with the standard defect reconstruction modalities (study specific aim 5);
- Data presentation at international/national research meetings.
- Manuscript preparation and submission to a high-impact-factor peer-reviewed journal.

Milestone #5: Data presentation in research forums

Milestone #6: Manuscript publication

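### Healing without complications is the only outcome the trial is sized on, but no between-arm analysis is named for it and its stated precision is for one proportion on 30 patients

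*SAP*

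**What the plan says.** The trial randomises 30 patients, 15 to Masquelet and 15 to CTMC (Protocol, Treatment Arm Randomization). In the protocol's section on resources and cost-effectiveness, "the primary determination in the study is to establish whether applying one of the treatment arms versus the other is associated with" an improved outcome; no primary outcome is named there.

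Sample Size Justification, in both documents, rests on one outcome. It assumes that "75% of patients with segmental bone defects reconstructed with the CTMC technique will heal without complications". The number of patients is explained by practicality: "This sample size of 30 is largely determined by clinical feasibility". Precision is then given as "a two-sided 95% confidence interval for a single proportion using the large sample normal approximation will extend 0.134 from the observed proportion". No Masquelet rate, between-arm difference or power is stated.

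In the SAP's Statistical Methodology, and in the matching protocol section, that outcome appears only in a descriptive bullet: "estimate the proportion of healing with/without complications". The bullet does not mention arms. The same section plans a paired t-test and a mixed model for repeated measures of Masquelet against CTMC on outcome measures that it does not list.

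The protocol's cost-effectiveness section adds two comparisons that the SAP does not carry over. One is that "Frequencies of repeat surgical intervention and complications will be compared with chi-square tests". The other is a log-rank test and proportional hazards model for the progression of healing.

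After completion, the protocol's Study Time Frame lists this task: "Establishing the clinical indications and treatment recommendation for CTMC the based upon the treatment outcome".

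**The concern.** A randomised comparison needs a stated contrast on the outcome that justified its size. Here that outcome has a rate assumption and a precision target, but no named method for setting one arm against the other. Two gaps combine.

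First, an analyst following the SAP would have to choose the between-arm analysis of healing without complications after seeing the data. The only tests on offer are built for paired or repeated measurements.

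Second, the precision a reader sees is that of a single proportion on 30 patients, although no single treatment is given to 30 patients. The 75% belongs to CTMC, and the question is the difference between CTMC and Masquelet. The printed figure therefore suggests more information than the randomised contrast holds. The closing task on a CTMC recommendation does not itself say that it rests on that contrast.

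**Working it through.** **Inputs**

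- Rate 0.75, stated for CTMC only (Sample Size Justification, both documents).
- Total 30 (same section); 15 per arm (Protocol, Treatment Arm Randomization).
- Two-sided 95%, normal approximation, so z = 1.96 (same sample-size section).
- Masquelet rate: not given in either document. Values of 0.75 and 0.50 are assumed for the half-widths, and a wider range for power.

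**1. The plan's own figure**

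Half-width = 1.96 × √(p(1 − p)/n), with p(1 − p) = 0.75 × 0.25 = 0.1875.

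- n = 30: 1.96 × √(0.1875/30) = 1.96 × 0.0791 = 0.155.
- The printed 0.134 is not reproduced. It corresponds to n = 40: 1.96 × √(0.1875/40) = 0.134.

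That slip is a separate matter. Correcting it to 0.155 would still give a one-sample precision, so 0.155 is the reference below.

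**2. The group to which the 75% applies**

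One arm of 15: 1.96 × √(0.1875/15) = 1.96 × 0.1118 = 0.219.

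**3. The comparison the trial is designed to make**

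Half-width of the difference = 1.96 × √(p₁(1 − p₁)/15 + p₂(1 − p₂)/15).

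- 75% in both arms: 1.96 × √(2 × 0.1875/15) = 1.96 × 0.1581 = 0.310.
- 75% v an assumed 50%: 1.96 × √(0.1875/15 + 0.25/15) = 1.96 × 0.1708 = 0.335.

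At equal rates this is exactly twice the one-sample value on 30, because 2/15 = 4/30 and √4 = 2. Against the printed 0.134 the ratio is 0.310/0.134 = 2.3.

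**4. What that means in practice**

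If the arms came out equal at 75%, true differences of up to about 31 percentage points in either direction would remain compatible with the data. For illustration, Fisher's exact power at an assumed two-sided 0.05, with CTMC at 75% and 15 per arm, is:

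| Assumed Masquelet rate | Power |
|---|---|
| 60% | 6% |
| 50% | 16% |
| 40% | 33% |
| 25% | 68% |

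By the normal approximation, about 80% power needs a Masquelet rate near 26%, a difference of about 49 points. The plan claims no power, so these figures contradict nothing in it. They show only how large a difference has to be before this trial can resolve it.

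**5. Which planned analysis reaches the outcome**

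| Planned analysis | Where | Compares arms on healing without complications? |
|---|---|---|
| Descriptive proportion | SAP and protocol | Names the outcome; arms not mentioned |
| Paired t-test | SAP and protocol | Compares arms on unlisted measures; assumes pairs, but patients are randomised individually |
| Mixed model for repeated measures | SAP and protocol | Compares arms on unlisted measures; not specified for a single yes/no result |
| ANCOVA | SAP | No; compares graft options within arms |
| Chi-square | Protocol only | One component: complications |
| Log-rank and proportional hazards | Protocol only | The other component: progression of healing |

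The component tests do not add up to the combined outcome. A patient can heal with a complication, or have no complication and fail to heal.

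**The case against.** The best case for the plan has four parts.

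- **Both components are compared.** Complications have a chi-square test and healing progression a log-rank test, with outcome analyses done both by intention to treat and on an efficacy basis. This is correct. A reader might infer that the arms are never compared on anything bearing on this outcome, or that randomisation adds nothing to it. The documents do not support either reading.
- **The unlisted outcome measures could include it.** Nothing excludes it from the t-test or the mixed model. The protocol's data and safety monitoring plan also speaks of comparing healing rates descriptively and of ANCOVA between arms, and its second aim is to compare the efficacy of the two techniques. This stands as evidence of intent to compare. It does not name a method that fits a yes/no result in independent arms.
- **The descriptive bullet does not say pooled.** Also correct. The single proportion on 30 occurs only in the sample-size text. A reader might infer that one pooled rate will be reported, or that CTMC will be judged against the preliminary series' 75%. Neither is planned anywhere, and reporting by arm is at least as natural a reading.
- **The sample size is openly a matter of feasibility.** True, and no power is claimed. The plan does state a precision, however, and that precision describes neither arm nor their difference.

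The list of post-completion tasks also includes full analysis for the comparative aims, so its CTMC-only item does not replace the comparison of arms. That item simply leaves the link unstated.

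**Conclusion.** The point holds as a gap in specification and a mismatch in precision, not as the absence of any comparison. Neither document names a between-arm test or interval for the one outcome used to size the trial. The SAP omits the two component comparisons that the protocol makes, and its remaining between-arm methods are unsuitable for this outcome.

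At the plan's own 75%, the uncertainty of the randomised contrast is about twice that of a correctly calculated single proportion on 30 patients. The between-arm values rest on 15 evaluable patients per arm, the normal approximation, and assumed Masquelet rates, since the documents supply none. Any loss to follow-up would widen them.

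This should be corrected. It does not undermine the data collection or the randomisation.

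**What to change.** - **Statistical Methodology, protocol and SAP.** State that the proportion healed without complications will be reported by arm as randomised. Compare the arms by the risk difference (CTMC minus Masquelet) with a 95% Newcombe or Miettinen-Nurminen interval. The sponsor should fix the assessment time in advance from the existing visit schedule, for example the final 18-month visit.
- **Definitions.** The sponsor also needs to state what counts as healed and what counts as a complication, because the risk difference cannot be calculated without them. Those choices are the sponsor's.
- **Sample Size Justification, protocol and SAP.** Give the expected between-arm half-width, about 0.31 at 75% in both arms, as the precision for the comparison. Label any Masquelet rate as an assumption, and say that only very large differences can be excluded.
- **Study Time Frame, post-completion tasks.** State that any conclusion about CTMC on this outcome rests on the contrast with Masquelet.

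The cost is a few sentences in each document and one simple additional analysis, with no new patients or data collection. The downside is that the stated precision looks less favourable than the present figure.
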